4.3. Analyses of Secondary Outcomes

4.3.1. Time to intubation or death

The time to intubation for mechanical ventilation will be analyzed using a cause-specific Cox regression model with censoring occurring at the time of discharge (Kalbfleisch and Prentice, 2011). That is, individuals who are intubation-free and alive at the time of discharge will have their follow-up censored at the time of hospital discharge. The regression coefficient and associated standard error from the cause-specific Cox regression model for intubation or in-hospital death will be used to compute an estimate of the cause-specific hazard ratio along with a 95% confidence interval and a p-value.

To accompany this analysis, estimates of the cumulative incidence functions for the composite event of intubation or death will be plotted for each arm

4.3.2. Ventilator-free days

The total number of ventilator-free days will be computed for each individual between randomization and Day 30. For each treatment group, the mean ventilator-free days will be computed by the sample average, and an associated robust bootstrap standard error will be obtained by resampling with replacement from the respective arm $B=200$ times. The difference in the sample means will be computed, along with a 95% confidence interval obtained based on the robust standard errors. A Wald test of the null hypothesis that there is no difference in the mean ventilator-free days between groups will be carried out using a robust variance obtained from the individual bootstrap standard errors.

4.3.3. In-hospital death by Day 90

The probability of in-hospital death within 90 days of randomization will be estimated for each treatment group by the proportion of individuals randomized to each group who died in hospital within the first 90 days of study. The primary analysis will be based on a 2-sided Wald test of the null hypothesis that probability of death by 90 days is the same among individuals

receiving CCP or standard care. The percent relative risk reduction will be estimated along with a 95% confidence interval and a p-value of the null hypothesis will be computed.

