1.3. Sample Size Justification

Assuming a 30% risk of the composite outcome of intubation or death by Day 30 among hospitalized patients under standard of care, a sample size of 1200 individuals (800 in the CCP arm, and 400 in the standard of care arm) will provide 80% power ($\beta = 0.20$) to detect a relative risk reduction of 25% with CCP therapy using a 2-tailed test at level $\alpha = 0.05$. We assume that no patient will be lost to follow-up.

2. Responses

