4.3.6. Length of stay in intensive care unit

The total number of days in the intensive care unit (ICU) will be computed for each individual over the 30-day period from the time of randomization. For each treatment group, the mean number of ICU days will be computed by the sample average, and an associated robust bootstrap standard error will be obtained by resampling with replacement from the respective arm B=200 times. The difference in the sample means will be computed, along with a 95% confidence interval obtained based on the robust standard errors. A Wald test of the null hypothesis that there is no difference in the mean number of ICU days between groups will be carried out using a robust variance obtained from the individual bootstrap standard errors.

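### Ventilator-free days and ICU days are tested with a standard error from only 200 bootstrap resamples of a mean, so the random seed alone can move a borderline p-value between about 0.03 and 0.07

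*SAP*

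**What the plan says.** SAP 4.3.2 (Ventilator-free days) averages the days in each arm and attaches a bootstrap standard error to each average. The number of resamples is fixed at 200 per arm: "resampling with replacement from the respective arm $B=200$ times". The 95% confidence interval for the difference uses these standard errors, and the Wald test "will be carried out using a robust variance obtained from the individual bootstrap standard errors".

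SAP 4.3.6 (Length of stay in intensive care unit) repeats the scheme for ICU days. The resampling is again "resampling with replacement from the respective arm B=200 times", and the inference is "A Wald test of the null hypothesis that there is no difference in the mean number of ICU days between groups".

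Neither section states a random seed or explains why a sample mean needs a bootstrap. SAP 4.3.12 (Incremental cost per QALY) uses 1,000 resamples for the interval around the cost-effectiveness ratio. Protocol 12.4.2 makes no multiplicity adjustment for secondary outcomes.

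**The concern.** The variance of a sample mean needs no simulation. As the number of resamples grows, the bootstrap standard error of a mean converges to the plug-in formula, which is s/√n apart from a factor √((n−1)/n) that is negligible at n = 400 or 800. Resampling within each arm and adding the two variances therefore aims at sqrt(s1²/n1 + s2²/n2), the ordinary unequal-variance standard error.

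The SAP then refers the result to a normal distribution. It uses no percentile interval or other bootstrap feature that would respond to the skewness of these outcomes. So the bootstrap adds no robustness over the closed form. It adds only simulation noise, and at 200 resamples that noise is visible in the p-value.

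At stake are the p-value and confidence interval for two prespecified secondary outcomes of an open-label trial. Their nominal p-values will be read directly because there is no multiplicity adjustment. Two analysts who follow the plan exactly on the same data can make opposite significance statements. With no seed fixed in advance, there is also room for re-running, or for the appearance of it.

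**Working it through.** **Inputs**

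- Resamples: B = 200 per arm (SAP 4.3.2 and 4.3.6).
- Arm sizes: "a sample size of 1200 individuals (800 in the CCP arm, and 400 in the standard of care arm") (SAP 1.3).
- Outcome standard deviations: not given. Equal SDs are assumed first, then varied. The result depends on B and on each arm's share of the variance, not on the size of the SD.

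**The plan's own figure.** SAP 1.3 states 1,200 patients for 80% power, two-sided α = 0.05, 30% in controls and a 25% relative reduction (0.75 × 30% = 22.5%). With pooled proportion (0.30 + 2 × 0.225)/3 = 0.25 and 2:1 allocation:

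n(control) = [1.96 √(0.25 × 0.75 × 1.5) + 0.8416 √(0.30 × 0.70 + 0.225 × 0.775/2)]² / 0.075² ≈ 399.1, taken as 400.

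The total is 1,200 and the power is 80.1%. The arm sizes reproduce. The documents give no figure for ventilator-free or ICU days to compare with.

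**Step 1: noise in one arm.** A bootstrap variance from B resamples is approximately the true variance × χ²(B−1)/(B−1). Its coefficient of variation is √(2/199) = 10.0%, so the standard error varies by half of that, 5.0%.

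**Step 2: noise in the difference.** With equal SDs the variance shares are (1/800)/(1/800 + 1/400) = 1/3 for CCP and 2/3 for standard of care. The coefficient of variation of the summed variance is √[(1/9 + 4/9) × 2/199] = 7.5%, so the standard error has a Monte Carlo SD of 3.7%.

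**Step 3: effect on a borderline p-value.** Take a difference with exact z = 1.96 (p = 0.050). The standard error ranges over 1 ± 1.96 × 0.037, or about 0.93 to 1.07 times its exact value. The reported z then runs from about 2.11 down to 1.83, and p from about 0.034 to 0.068. Simulation of the chi-square model gives 0.0345 to 0.0678 (95% range) and 0.030 to 0.074 (99% range).

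**Step 4: other variance shares**, exact p = 0.050, B = 200:

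| Share of variance, smaller/larger | 95% range of reported p |
|---|---|
| 50/50 | 0.035–0.067 |
| 33/67 (equal SDs) | 0.035–0.068 |
| 20/80 | 0.033–0.070 |
| 10/90 | 0.032–0.072 |
| one arm supplies all | 0.030–0.074 |

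**Step 5: crossing 0.05** (equal SDs)

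| Exact p | Reported on the other side of 0.05 | Two seeds disagree |
|---|---|---|
| 0.045 | 26% | 2 × 0.26 × 0.74 ≈ 39% |
| 0.050 | – | 50% |
| 0.055 | 30% | 2 × 0.30 × 0.70 = 42% |

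Any exact p between about 0.035 and 0.069 can cross 0.05 within the 95% Monte Carlo limits.

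**Step 6: check with real bootstraps.** On an assumed skewed 0–30 day dataset (800 and 400 patients, SDs 8.8 and 10.0) with the difference set at exact p = 0.05, 4,000 seeds gave a 95% range of 0.034 to 0.069, a minimum of 0.023 and a maximum of 0.085. About 51% of seeds gave p < 0.05. In a separate simulated ventilator-free-day dataset, the closed-form standard error was 0.556 and the bootstrap averaged 0.555 with a coefficient of variation of 3.9%. The bootstrap is therefore centred on the closed form.

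**Step 7: more resamples** (equal SDs, exact p = 0.050)

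| B | 95% range of reported p |
|---|---|
| 200 | 0.035–0.068 |
| 1,000 | 0.043–0.058 |
| 2,000 | 0.045–0.055 |
| 10,000 | 0.048–0.052 |
| closed form | no dependence on seed |

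**The case against.** The strongest reply is that this rarely matters. The figures above are conditional on a borderline result. Averaged over all results in the same model, the 200-resample test disagrees with the exact-standard-error test in 0.7% of trials under no effect, 1.6% at 80% power and 2.3% at 50% power, the worst case. Two analysts disagree in 1.0% to 3.3% of trials. An exact p of 0.03 stays below 0.05 in 99.8% of runs, and an exact p of 0.07 stays above it in 98%. Type I error is 0.0507 against 0.0499, and power is unchanged. The point estimate does not involve the bootstrap. The primary test, interim boundary, conditional power and sample-size re-estimation do not use it either. All of this stands, and it keeps the point minor.

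Three further replies carry partial weight:

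- The 1,000 resamples for the cost-effectiveness ratio may only reflect a harder statistic, so that contrast is weak evidence of inconsistency. The case does not rest on it.
- A seed is often left to the programming specification. But a seed only makes the number repeatable; the 3.7% error remains.
- Protocol 12.4.2 names a nonparametric comparison for ventilator-free days and Cox regression for ICU stay, whereas the SAP tests means. Which method governs could matter more than seed noise. That is a separate discrepancy to reconcile, and it does not make the bootstrap in the SAP adequate.

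None of these gives a reason to prefer 200 resamples to an available formula.

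**Conclusion.** The concern holds, as a minor point. At the planned arm sizes the method in SAP 4.3.2 and 4.3.6 adds about 3.7% Monte Carlo error to the standard error, and to the confidence-interval half-width, with essentially no bias and no gain in robustness. A result that is exactly at p = 0.050 is reported between about 0.034 and 0.068 depending on the seed.

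This rests on the chi-square approximation for a bootstrap variance, which real bootstraps on assumed skewed data confirmed, and on equal SDs. For the more unequal variance shares tried, the range widens to as much as 0.030 to 0.074; with equal shares it is marginally narrower. Only borderline secondary results are affected, and the primary conclusion is not.

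**What to change.** In SAP 4.3.2 and 4.3.6, replace the bootstrap standard error with sqrt(s1²/n1 + s2²/n2), where s and n are each arm's sample standard deviation and size. Use it for both the 95% confidence interval and the Wald test. This estimates the same quantity and removes the dependence on a seed.

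If a bootstrap is kept, specify at least 10,000 resamples and a fixed seed written into the SAP. The 95% range at exact p = 0.050 then narrows to 0.048–0.052. A few thousand would already remove most of the noise (0.045–0.055 at 2,000), but the larger number costs only seconds of computing.

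While these sections are open, state which document's method governs the two outcomes, given the different tests in Protocol 12.4.2.

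The cost is a wording change in the SAP. No patients, data or trial procedures are affected.

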4.3.4. Time to in-hospital death

The time to in-hospital death will be analyzed using a cause-specific Cox regression model to deal with the competing risks of discharge from the hospital in which the individual was randomized; for subjects hospitalized for more than 90 days their time of in-hospital death will be censored at 90 days. That is, individuals who did not die in the hospital they were admitted to at the time of randomization will have their follow-up censored at the time of discharge from this hospital. The regression coefficient and associated standard error from the cause-specific Cox regression model for death in the original hospital will be used to compute an estimate of the cause-specific hazard ratio along with a 95% confidence interval and a p-value. To accompany this analysis estimates of the cumulative incidence functions will be plotted for in-hospital death and discharge for each treatment group.

4.3.5. Death by Day 30

The probability of death between randomization and Day 30 will be estimated for each treatment group by the proportion of individuals randomized who died between randomization and Day 30. The test will be based on a 2-sided Wald test of the null hypothesis that the probability of death by Day 30 is the same among individuals receiving CCP or standard of care. The percent relative risk reduction will be estimated along with a 95% confidence interval and a p-value of the null hypothesis will be computed.

4.3.6. Length of stay in intensive care unit

The total number of days in the intensive care unit (ICU) will be computed for each individual over the 30-day period from the time of randomization. For each treatment group, the mean number of ICU days will be computed by the sample average, and an associated robust bootstrap standard error will be obtained by resampling with replacement from the respective arm B=200 times. The difference in the sample means will be computed, along with a 95% confidence interval obtained based on the robust standard errors. A Wald test of the null hypothesis that there is no difference in the mean number of ICU days between groups will be carried out using a robust variance obtained from the individual bootstrap standard errors.

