12.4.2. Secondary Endpoints

A cause-specific Cox regression model will be fitted for the intubation-free survival time defined as the first of the times of intubation or death with censoring at discharge or 30 days whichever comes first. A hazard ratio and 95% confidence interval will be computed from this fitted model.

Cumulative incidence functions will be estimated and plotted for each treatment arm for the time to intubation or death.

The restricted mean number of ventilator-free days over the first 30 days will be compared between the two groups based on a nonparametric tests.

The time to in-hospital death will be analyzed using a cause-specific Cox regression model treating the minimum of the time of discharge and 90 days as the censoring time. A hazard ratio and 95% confidence interval will be computed from this fitted model. Cumulative incidence functions will be estimated and plotted to estimate the proportion of patients who died during the initial hospitalization up to 90 days from randomization.

Finally, the survival status of individuals will be recorded at day 30 and the proportion of individuals who have died will be computed for each arm with a two-sample Wald test carried out based on the proportions.

Length of hospitalization over 90 days and length of stay in the ICU over 30 days will be modeled using a Cox regression without any distinction between reasons for discharge.

The proportion of patients needing ECMO over 30 days will be compared between the two arms based on a two-sided test of the difference between proportions.

The proportion of patients needing renal replacement therapy over the first 30 days will be compared between the two arms based on a Wald test.

The proportion of patients developing myocarditis over the first 30 days will be compared between the two arms based on a Wald test.

The change in EQ-5D-5L utility value from baseline will be compared between the two arms.

Incremental cost per quality-adjusted life year between the CCP and standard care over the 30-day time horizon.

No multiplicity adjustments will be implemented for the secondary analyses. Procedures for addressing missing data will be described in the SAP.

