2.2.2. Ventilator-free days

The number of ventilator-free days between randomization and Day 30 will be computed as the number of days during this 30-day period of time during which they were alive and not requiring ventilation. This total number of days could be made up days prior to ventilation and the number of days after discontinuation of ventilation if ventilation is required. Patients will be contacted at Day 30 by telephone to determine whether there were any ICU admissions since discharge from the hospital they were in at the time of recruitment. Patients discharged from hospital will be assumed to be off-ventilator post-discharge unless otherwise indicated.

2.2.3. In-hospital death by Day 90

This response will be a binary indicator of whether a patient died in-hospital within 90 days of randomization.

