2.2.6. Length of stay in intensive care unit

The number of days spent in the intensive care unit (ICU) over the 30-day period following randomization will be recorded. This total number of ICU days could be made up days from multiple admissions within the 30-day period from randomization if they are discharged and re-admitted a second time within this 30-day period. Patients will be contacted at Day 30 by telephone to determine whether there were any hospital admissions since discharge from the hospital they were in at the time of recruitment. Patients discharged from hospital will be assumed not to be in an ICU elsewhere, unless otherwise indicated.

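### Mean ICU days are compared with no rule for death, so if patients who die have shorter ICU stays than survivors and CCP averts few ICU admissions, a mortality benefit would appear as more ICU days on CCP

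*SAP*

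**What the plan says.** SAP 2.2.6 defines the outcome: "The number of days spent in the intensive care unit (ICU) over the 30-day period following randomization will be recorded". Days from several ICU admissions within the window are added together. The only default for unobserved time concerns discharge: "Patients discharged from hospital will be assumed not to be in an ICU elsewhere, unless otherwise indicated". Death is not mentioned. SAP 4.1 deals with withdrawal and missing data, not with death.

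SAP 4.3.6 then compares the arms: "the mean number of ICU days will be computed by the sample average", with bootstrap standard errors from 200 resamples and "A Wald test of the null hypothesis that there is no difference in the mean number of ICU days between groups".

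Two other places bear on this:

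- SAP 2.2.2 counts ventilator-free days only while patients are "alive and not requiring ventilation". The analysis in SAP 4.3.2 is otherwise the same as for ICU days.
- Protocol 12.4.2 plans another analysis: "length of stay in the ICU over 30 days will be modeled using a Cox regression without any distinction between reasons for discharge".

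Protocol 3.1 gives the outcome a direction. It lists ICU length of stay, with ICU admission and hospital stay, among the outcomes that CCP is expected to improve.

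**The concern.** A patient who dies on the fifth ICU day contributes 5 days; one who recovers after fourteen contributes 14. A patient who dies on the ward contributes 0, like one who goes home without ever needing ICU. Fewer ICU days can therefore mean faster recovery or earlier death, and the planned comparison cannot tell them apart.

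Within one SAP, death lowers the score on ventilator-free days but can improve the score on ICU days, under otherwise matching analysis text. Because Protocol 3.1 reads a shorter ICU stay as benefit, the estimate could point the wrong way on a listed secondary outcome that has its own confidence interval and test.

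The conflict between the documents does not rescue either method. In a Cox model that ignores the reason for leaving ICU, a death is an exit like any other, so earlier deaths also look like shorter stays.

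**Working it through.** **Inputs.** The documents give no ICU admission rate, ICU mortality, ICU stay or standard deviation, so there is no planned figure for this outcome to reproduce. From the SAP come only the arm sizes: 800 CCP and 400 standard of care. (The trial's 1200 patients and 80% power for the primary outcome do reproduce, at 80.1% with pooled variance, and are not affected.) Assumed for illustration:

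- ICU admission 35% in both arms.
- Mortality 18% on standard of care and 13.5% on CCP (a 25% relative cut), all deaths occurring in ICU.
- ICU survivors stay 14 days; decedents stay L days in ICU.

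**Mean ICU days** = (deaths × L) + (ICU survivors × 14). ICU survivors are 35% − 18% = 17% and 35% − 13.5% = 21.5%.

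At L = 7:

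- Standard of care: 0.18 × 7 + 0.17 × 14 = 3.64
- CCP: 0.135 × 7 + 0.215 × 14 = 3.955
- Difference: +0.315 day, so CCP looks worse.

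With equal admission, the difference reduces to 0.045 × (14 − L):

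| Decedent ICU stay L | Standard of care | CCP | CCP minus standard |
|---|---|---|---|
| 3 | 2.92 | 3.415 | +0.495 |
| 7 | 3.64 | 3.955 | +0.315 |
| 12 | 4.54 | 4.63 | +0.09 |
| 14 | 4.90 | 4.90 | 0 |
| 18 | 5.62 | 5.44 | −0.18 |

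**Days alive and outside ICU at L = 7.** Assume further that each death loses 20 of the 30 days. The score is 30 − ICU days − 20 × deaths:

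- Standard of care: 30 − 3.64 − 3.60 = 22.76
- CCP: 30 − 3.955 − 2.70 = 23.345
- Difference: +0.585 day in favour of CCP, the opposite conclusion from raw ICU days.

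**If CCP also averts ICU admissions (L = 7).** Hold CCP deaths at 13.5% and let the averted admissions be 14-day survivors. The arms are equal when 0.945 + 14s = 3.64, so s = 0.1925. CCP admission is then 0.135 + 0.1925 = 32.75%, a relative cut of 0.0225 / 0.35 = 6.4%. With a 25% cut in admission (to 26.25%, leaving 12.75% ICU survivors), CCP has 0.945 + 0.1275 × 14 = 2.73 ICU days against 3.64 and looks better.

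**Size against noise.** With stays fixed at these values, the variances at L = 7 are 0.18 × 49 + 0.17 × 196 − 3.64² = 28.9 and 0.135 × 49 + 0.215 × 196 − 3.955² = 33.1. The standard error of the difference is √(28.9/400 + 33.1/800) = 0.34 day, so the shift is about 0.9 standard error. The same calculation gives about 1.5 at L = 3 (0.495/0.325) and 0.2 at L = 12 (0.09/0.383). Real spread in stays would enlarge the standard errors and lower these ratios.

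**A second assumed set.** Take ICU admission q of 20% or 30% in both arms, ICU mortality 50% v 37.5%, and survivors at 14 days. The difference is q × 0.125 × (14 − L). For L from 8 down to 3 it runs from 0.2 × 0.125 × 6 = +0.15 to 0.3 × 0.125 × 11 = +0.41 day on CCP. The direction and order of size agree with the first set.

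**The case against.** A reader might infer that preventing deaths always counts against CCP on this outcome. The documents do not support that. They give no ICU figures from which a sign could be derived. Protocol 3.1 expects CCP to lower the risk of ICU admission as well, and the trial is powered for a 25% relative cut in intubation or death. If admission fell by anything like that proportion, mean ICU days would favour CCP on the inputs above. Deaths after long ICU stays also reverse the shift.

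The other arguments for leaving the plan alone are these:

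- The shift is small against sampling error and unlikely to be significant by itself. This stands.
- Death is visible elsewhere: in the primary composite, Day-30 death, Day-90 in-hospital death, time to in-hospital death and ventilator-free days. This stands, and it limits the harm, but it does not make the ICU estimate interpretable alone.
- Not separating death from discharge is the authors' stated convention for lengths of stay (Protocol 12.4.2; SAP 4.3.7 for hospital stay), and mean ICU days in all randomized patients is a well-defined quantity that suits costing. This stands for resource use. It does not justify reading fewer days as clinical benefit, which is what Protocol 3.1 does.
- The alternative outcome is imperfect too. Days outside ICU before death still count: a ward death on Day 25 scores about 24, while a survivor with 14 ICU days scores 16. This also stands, and the fix has to allow for it.

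**Conclusion.** The point holds as a conditional one. The SAP compares raw ICU days with no rule for death, departs from its own convention for ventilator-free days, and disagrees with the protocol on method. If decedents have shorter ICU stays than survivors and CCP averts few ICU admissions, a mortality benefit raises mean ICU days on CCP. On the first assumed set the rise is about 0.1 to 0.5 day for decedent stays of 12 down to 3 days, or roughly 0.2 to 1.5 standard errors with no spread in stays. It is zero at equal stays, reverses at longer decedent stays, and at 7 days is cancelled by about a 6% relative cut in ICU admission. Every ICU input is an assumption, so these sizes are illustrations and not predictions. The consequence is confined to the interpretation of one secondary outcome without multiplicity adjustment; the primary analysis and sample size are untouched. The change is worth making because it is cheap.

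**What to change.** 1. In SAP 2.2.6 and 4.3.6, make days alive and outside ICU to Day 30 the ICU comparison used to judge benefit. Apply the alive convention of SAP 2.2.2 and the bootstrap and Wald test already specified.
2. State that it will be read beside Day-30 death, because days outside ICU before death still count.
3. Keep raw mean ICU days by arm as a descriptive resource-use measure. The cost analysis in SAP 4.3.12 (incremental cost per QALY) uses ICU stay.
4. Align Protocol 12.4.2 with the SAP. Keeping the Cox model instead would not solve the problem.

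**Cost.** This is a small amendment to the protocol and SAP for one listed secondary outcome, which Protocol 11.8 requires to go through the amendment process. ICU admission is recorded daily in hospital. The new outcome needs nothing that ventilator-free days and raw ICU days, as already defined, do not need. However, the Day-30 list in Protocol 8.8 names vital status and readmission, without a date of death or ICU days after discharge. The sponsor should confirm that both are captured for patients discharged before Day 30.
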